The informed consent will be checked (the purpose of checking the consent is to assure that the subject is still interested in the study and they are still eligible to be in the study which will also be another form of an AE screening) along with a review of the medical history. Impressions of the subject upper and lower jaws will be taken with alginate for preparation of study models and surgical guides. Bite registration will be taken with a silicone material. Clinical measurements will be taken, including probing depth, gingival recession, plaque index, gingival index, keratinized mucosa width, and the PES score. A standardized peri-apical film will be taken along with clinical photos. Eligible subjects will be randomly assigned to one of the two groups after V3.

Implant and bone surgery (V4)

The informed consent will be checked along with a review of the medical history. The blood pressure and heart rate will be checked before surgery. The area selected for surgery will be locally anesthetized and examined. The hopeless tooth will be extracted under local anesthesia, without raising a flap. If necessary, a small flap might be elevated to facilitate the extraction. For subjects with intact buccal plate (equal or less than 4 mm loss), an implant will be placed according to the manufacturer's protocol for both groups. The implant position follows the computerized surgical guides (Neoguide, Neobiotech, South Korea) that are designed based on the CBCT scans. The gap between the implant and socket wall will be filled with bone allografts (The tooth root dimension is most of the time larger than the implant). In cases with a small buccal wall defect, a collagen membrane will be used. The test implants will be restored immediately with a provisional crown, which will be replaced by a permanent crown. A healing abutment and collatape to contain bone grafts

will be placed for control implants but without immediate restoration during the healing period. A removable temporary denture may be provided at subject request. All surgical procedures will be performed by a periodontist. Implant stability will be assessed at the time of placement. Any adverse events such as no implant stability, etc. during the surgery will be reported. Clinical measurements will be taken including: socket-related and implant-related parameters. A standardized peri-apical radiograph will be taken, as well as clinical photos.

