Subjects who lose more than 4mm of buccal plate after extraction will be excluded from the study at this time. They will receive bone allografts and collagen membrane as a socket grafting material. The test implant that does not achieve 30 N-cm will be treated as a control implant and excluded from the study.

Post-op visits after implant and bone surgery (V5, V6, V7 if necessary)

Post-op visits will be scheduled at 14 ± 3 days, 28 ± 3 days, and varied date upon subject oral condition, if needed. The informed consent along with a review of the medical history will be checked at each visit. Clinical measurements will be taken, including: mid-facial mucosal level, papilla height and labial ridge contour. Clinical photos will be taken during the visit. The

wound will be gently debrided and disinfected. Sutures, if any, will be removed.

Additional post-op visits (V7) may be necessary for conditions that require additional care for subject safety, such as premature wound exposure, minor infection, and slower healing. They are based on per subject needs for a visit, not for every subject and will be followed as adverse events. No clinical measurements will be taken at this visit.

Management of adverse events

If the dental implant does not achieve primary stability (10-20 % of prevalence rate) due to infection or other reasons, the implant will be removed in a brief surgery. The osteotomy site will be grafted with allograft bone and covered by a collagen membrane. The wound will be closed with sutures. The participants with the abovementioned conditions will be withdrawn from the study.

Alternative treatments will be given. All adverse events will be reported.

Crown impression (V9)

The impression visit will be at 4 (+/- 1) months after the baseline surgery, depending on the healing of the bone graft and implant. The informed consent will be checked along with a review of the medical history. Any adverse events will be screened and reported. If the implant fails, it will be removed and the site will be grafted at no charge. The subjects with a failed implant will be excluded. Impressions will be taken for upper and lower jaws with alginate and silicone materials, along with a bite registration.

Crown placement (V10)

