The final crown placement will be within several weeks from the impression. The informed consent will be checked along with a review of the medical history. Any adverse events will be screened and reported. If the implant is loose then the subject will be taken out of the study. The implant will be removed and bone placed where the implant was at no charge to the subject. Their participation in the study will be over at this time.

Clinical measurements, including PES/WES, mid-facial mucosal level, papilla height, and labial ridge contour will be taken. All components to be used will be commercially available from Neobiotech. A standardized radiograph and

intraoral photos will be taken. Multiple visits may be required to assure the quality of crowns.

Crown follow-up/Final visit (V11)

One crown follow-up visit will be scheduled at 10 (+/- 2) months after the baseline surgery. A standardized peri-apical film, clinical measurements, clinical photos and impressions/bite registration will be done. The clinical measurements include probing depth, plaque index, gingival index, keratinized mucosa width, PES/WES, mid-facial mucosal level, papilla height and labial ridge contour. The informed consent will be checked along with a review of the medical history. Any adverse events will be screened and reported.

Schedule of Events

Event	Screening	CBCT scan	Pre-implant placement	Implant and bone surgery	Post-Op visit 1	Post-Op visit 2	Additional post-Op visits (if necessary) (c)	CBCT scan	Crown impression (IP)	Crown Placement	Crown follow-up/ Final Visit
	V1	V2	V3	V4	V5	V6	V7	V8	V9	V10	V11
Timeline				Baseline (BL)	14 D (+/- 3D)	28 D (+/- 3D)	Varied		4 (+/- 1) M after BL	3+ wks after IP	10 (+/- 2) M after BL
Informed consent	SIGN		X	X	X	X	X		X	X	X
Check BP, HR	X			X							
Med history review	X		X	X	X	X	X		X	X	X
Screen for adverse events				X	X	X	X		X	X	X
Eligibility Screen	X	X		X							
Impression and bite registration			X						X		X
CBCT Scan (a)		X						X			
Clinical measurements (b)			X	X	X	X				X	X
Periapical radiograph/ (S = Standardized)	X (optional)		X (S)	X (S)						X (S)	X (S)
Clinical photographs			X	X	X	X	X			X	X
Wound disinfection & suture removal (if any)					X	X	X				
Subject withdrawn by PI		Inadequate Bone		Inadequate Bone	Implant Loose	Implant Loose	Implant Loose		Implant Loose	Implant Loose	
Temp Crown for Test Group Only				X							
Bone Allograft				X							
Control Group – Temp Denture (at subject request)				X							

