(a) The dental school only does CBCTs on certain days and at certain times. For subject convenience the first CBCT may be scheduled at the pre-implant visit and the second CBCT may be scheduled at the implant uncover surgery. However, one or both, may be done at separate visits due to dental school CBCT scheduling. Additionally, for the convenience of the subject, the Screening, first CBCT Scan and Pre-implant visit can be combined on the same day.

(b) Clinical measurements consist of plaque Index, gingival Index, probing depth, recession, PES/WES, width of keratinized tissue, thickness of keratinized tissue, gingival margin level and socket- and implant-related features. Not all measurements will be made in each visit. Specific parameters for each visit will be listed in CRF.

(c) Schedule for these visits is based on a per subject need for a visit, not for every subject. Conditions that require additional care for subject safety, such as premature wound exposure and slower healing might require

additional visits and will be followed as adverse events

IV. Statistical Analysis

Sample Size

A power analysis was performed using a statistical power calculator. This study will have a sample size of 40 subjects, 20 in each of the two groups. We estimate to have 80% power (with a Type I error rate of 5%) to detect a mean difference of 0.8mm mucosal recession, with the estimated standard deviation of 0.8mm.²² This power calculation takes into account the estimated 10% of subjects drop out. A “p” value of less than 0.05 will be considered statistically significant.

Data Analysis

Mean values, standard deviations, and medians will be calculated for clinical and radiographic measurements. We will examine the univariate association of the defect size with the success of treatment using logistic regression. We will also attempt to examine the association of implant success with various combinations of clinical and radiographic parameters using multiple logistic regression, but acknowledge that we will be restricted by our sample size to at most two or three predictors in any model. Changes of the parameters over time within each group as well as differences between groups will be analyzed using the repeated measure of analysis of variance.

V. References

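### Papilla height and labial ridge contour have no named pre-treatment value, and gingival recession at V3 is not tied to the mid-facial mucosal level followed from day 14

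*Combined protocol and SAP*

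**What the plan says.** All places are in the combined protocol and SAP.

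- **Section III, Pre-implant placement visit (V3):** "Clinical measurements will be taken, including probing depth, gingival recession, plaque index, gingival index, keratinized mucosa width, and the PES score". Impressions are also taken: "Impressions of the subject upper and lower jaws will be taken with alginate for preparation of study models and surgical guides". Allocation follows: "Eligible subjects will be randomly assigned to one of the two groups after V3".
- **Section III, Implant and bone surgery (V4, labelled Baseline in the Schedule of Events):** "Clinical measurements will be taken including: socket-related and implant-related parameters". The provisional crown (test) or healing abutment (control) is placed at this visit.
- **Section III, Post-op visits (V5 at 14 days, V6 at 28 days):** "Clinical measurements will be taken, including: mid-facial mucosal level, papilla height and labial ridge contour".
- **Section III, Crown placement (V10):** "Clinical measurements, including PES/WES, mid-facial mucosal level, papilla height, and labial ridge contour will be taken".
- **Section III, Final visit (V11):** "The clinical measurements include probing depth, plaque index, gingival index, keratinized mucosa width, PES/WES, mid-facial mucosal level, papilla height and labial ridge contour".
- **Schedule of Events, footnote (b):** the general list includes "probing depth, recession, PES/WES, width of keratinized tissue, thickness of keratinized tissue, gingival margin level and socket- and implant-related features". It leaves the parameters for each visit to the CRF, which is not among the documents.
- **Section IV, Data Analysis:** repeated-measures ANOVA for change over time within each arm and for differences between arms. No baseline visit is named.
- **Section IV, Sample Size:** 20 per arm, 80% power, 5% type I error, 0.8 mm difference in mucosal recession, SD 0.8 mm, 10% dropout. The text does not say whether the SD is that of a level or of a change.

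**The concern.** Section II makes mucosal recession and esthetics the primary clinical outcomes, and recession is the only outcome that is powered. The Introduction motivates the trial by the possibility that immediate restoration preserves papilla height and the mucosal margin. These are questions about change from the state before treatment.

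The terms used before treatment and the terms used at follow-up do not meet in any one visit list. V3 has gingival recession but not mid-facial mucosal level. V5, V6, V10 and V11 have mid-facial mucosal level but not recession. Papilla height and ridge contour are named at neither V3 nor V4. The tooth is extracted at V4 and control implants carry no crown until V10, so a landmark on the tooth or crown cannot serve at every visit, and the text names no other.

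For a measure first taken at day 14, change over time starts after the arms have diverged. Tissue change before then is not in the series, and a missed pre-extraction measurement cannot be taken later.

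**Working it through.** **1. Where each measure is named in the visit text**

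| Measure | V3 (before allocation) | V4 (surgery) | V5, V6 | V10 | V11 | Footnote (b) |
|---|---|---|---|---|---|---|
| Gingival recession | yes | no | no | no | no | yes (as recession) |
| Mid-facial mucosal level | no | no | yes | yes | yes | gingival margin level |
| Papilla height | no | no | yes | yes | yes | no |
| Labial ridge contour | no | no | yes | yes | yes | no |
| PES | yes | no | no | yes (PES/WES) | yes (PES/WES) | yes (PES/WES) |

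PES has a named value before treatment and at the end. Recession has one before treatment under a term that is not used later. Papilla height and ridge contour have none. The stents described in section III are for standardising radiographs, not soft-tissue levels.

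**2. The plan's own figure**

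Inputs from Sample Size: difference 0.8 mm, SD 0.8 mm, 80% power, 5% type I error (two-sided assumed), 10% dropout. The two-sample t-test needs 16.7, so 17 per arm. 17 / 0.90 = 18.9, so 19 per arm and 38 in total, against 40 planned. The figure reproduces within two patients. With 20 × 0.90 = 18 completers per arm, the non-centrality is 0.8 / (0.8 × √(2/18)) = 3.0 on 34 df, and power is 83.0%.

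**3. What a same-scale V3 value would add for recession**

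Assumptions not in the documents: correlation r between V3 and V11 of 0.3, 0.5 or 0.7, and either reading of the 0.8 mm SD. With level SD = s:

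- V11 level alone: SD s, 34 df.
- V3-to-V11 change: SD s√(2(1−r)), 34 df.
- V11 with V3 as covariate: residual SD s√(1−r²), 33 df. Power is from 40,000 simulated trials per case, so chance imbalance at V3 is included.

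*Reading A, 0.8 mm is the SD of a level (s = 0.8):*

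| r | Change SD | V11 alone | Change | V11 with V3 covariate |
|---|---|---|---|---|
| 0.3 | 0.947 | 83.0% | 69.3% | 85.4% |
| 0.5 | 0.800 | 83.0% | 83.0% | 91.1% |
| 0.7 | 0.620 | 83.0% | 96.4% | 97.9% |

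*Reading B, 0.8 mm is the SD of a change (s = 0.8/√(2(1−r))):*

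| r | Level SD | V11 alone | Change | V11 with V3 covariate |
|---|---|---|---|---|
| 0.3 | 0.676 | 93.2% | 83.0% | 94.4% |
| 0.5 | 0.800 | 83.0% | 83.0% | 91.5% |
| 0.7 | 1.033 | 61.7% | 83.0% | 87.3% |

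The two r = 0.5 rows are the same case; 91.1% and 91.5% differ only by simulation error. The covariate form is highest in all six cases. Under reading A with r = 0 or 0.1 it gives 81.9% or 82.2% against 83.0%, a cost of about one percentage point.

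**4. What this does not measure**

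These figures show the gain from adjusting recession for a pre-treatment value. They do not show the loss from starting at day 14, which depends on how much tissue change occurs by then, and the documents do not say. For papilla height and ridge contour they give neither an SD nor a target difference, so no power can be computed.

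**The case against.** The strongest reply is that both primary domains already have a named measure before randomisation: gingival recession and PES are in the V3 list. That stands. A reader might infer that recession has no baseline at all, and the text does not support this. What recession lacks is a stated link to the later mucosal level and a shared landmark.

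The lists are also not closed. The V3 list is introduced by the word including, the schedule ticks clinical measurements at V3 and V4, a figure at the V3 heading is not shown, and footnote (b) defers to the CRF. The absence of papilla height and ridge contour from footnote (b) is weak evidence, since both are named at four visits and that list is therefore incomplete. All this stands, so the measures may be taken at V3 in practice. It does not supply the reference point or say which visit is the reference.

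A reader might also infer that day 14 is the planned baseline and that power suffers. For illustration, with the SD held at 0.8 mm, if 10%, 25% or 50% of a 0.8 mm difference had arisen by day 14, the power of a change from day 14 would be 75%, 59% or 31%. But Data Analysis does not name day 14 as the reference, and those shares are assumed. This is not the size of the problem.

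Nor is bias shown. Allocation follows V3, so the V11 difference between arms already includes any effect that arose before day 14. Under reading A, V11 alone has 83% power, above the 80% target.

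V3 casts exist, and photographs are taken at V3, V4, V5, V6, V10 and V11. No passage assigns either to measuring these outcomes. Impressions are planned only at V3, V9 and V11.

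**Conclusion.** The point holds in a limited form. Papilla height and labial ridge contour have no named value before treatment. Unless the CRF adds one, their change over time starts after the randomised treatment and omits change before day 14. The same applies to mid-facial mucosal level if V3 gingival recession is not used as its baseline, which the plan leaves unstated. The comparison of V11 levels between arms remains valid.

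The loss from a late start cannot be quantified from the documents. The benefit of a V3 covariate can be illustrated for recession only. Relative to V11 alone, it is about 2 to 15 points under reading A (85.4 − 83.0 to 97.9 − 83.0) and about 1 to 26 points under reading B (94.4 − 93.2 to 87.3 − 61.7). Both ranges rest on 18 completers per arm, a true difference of 0.8 mm and assumed correlations of 0.3 to 0.7. Confidence is medium, because the CRF and the V3 figure were not available. The change should be made: it alters what is collected at a visit that cannot be repeated once the tooth is out.

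**What to change.** 1. At V3, before extraction, record mid-facial mucosal level, papilla height and labial ridge contour from the same fixed reference used at V5 to V11. The adjacent teeth, required at entry, are one option. V3 and V11 casts can be the back-up for those two visits only.
2. State that the V3 value is the reference for recession, and say how V3 gingival recession relates to mid-facial mucosal level.
3. Compare the arms on V11 level with the V3 value as covariate, and likewise V11 PES with V3 PES. Report V3-to-V11 change descriptively.
4. Use the same terms in the V3 and V5 to V11 lists, footnote (b) and the CRF.

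The cost is a brief extra measurement at an existing visit, some protocol and CRF wording, and one degree of freedom. That is about one point of power or less if V3 and V11 prove nearly uncorrelated.

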A single center, randomized, controlled, parallel-arm study is planned to investigate esthetic outcomes after IIP + IIR in the esthetic zone. Forty adult patients who have a hopeless maxillary anterior or premolar tooth, with intact adjacent teeth will be enrolled. A signed written informed consent will be obtained after he or she has been given verbal and written information describing the nature and duration of the study. Subjects will not be screened or treated until an informed consent has been obtained. Patient information will be protected according to the privacy regulations of the federal Health Insurance Portability and Accountability Act of 1996 (HIPAA).

Enrolled patients will be randomly placed into one of two treatment groups, immediate implant placement and restoration group (IIR) or the IIP + delayed restoration group (DR). For all patients, the tooth will be extracted and an implant placed immediately. The subject will be randomly assigned before the surgery visit to either restoring the implant immediately (Test group) with a provisional crown or restoring the implant at 4 ± 1 month after implant placement (Control). Outcome analyses will be clinical and radiographic parameters to determine the esthetic outcomes of immediately restored IIP implants, in comparison to those immediately placed but restored in a delayed approach.

Study Protocol

I. Introduction

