Last but not the least, buccal plate thickness seems to be a determining factor for the stability of its overlying soft tissue. A thicker buccal plate might resist bone resorption more effectively.¹⁴ Furthermore, it is suggested at least 2 mm

thick crestal bone might be necessary for a stable dimension of facial mucosa.¹⁵ Unpredictable bone remodeling after immediate implant placement, especially in situations where there is a buccal wall defect, might be one of the reasons for seeing advanced soft tissue recession.¹⁶

Immediate implant restoration (IIR) is defined when an implant is restored within 48 hours after implant placement.¹⁷ With adequate implant primary stability, an implant can be restored immediately, however, it might be wise to leave it out of occlusion during the healing phase to allow for proper formation of osseointegration. The greatest advantage of this approach is to restore esthetics immediately. The responses of soft and hard tissues to this approach have been studied to some extent. A recent systematic review¹⁸ suggested that the timing of the restoration does not influence marginal bone level around implants. However, IIR might preserve the height of papilla¹⁹ and the level of mucosal margin.³ Therefore, IIR of immediately placed implants might improve the esthetic outcomes.

II. Objectives

The primary objective of this study is to evaluate the effect of IIR on clinical outcomes (mucosal recession and esthetics) of IIP implants, compared with the effect of DR on clinical outcomes of IIP implants. Essentially, we are testing whether a temporary crown placed right after the surgery will have better clinical outcomes than not placing one. Secondary outcomes will include radiographic marginal bone changes.

III. Treatment

A. Patient selection

Forty patients will be randomized into two experimental groups: 20 in the test group (IIR) and 20 in the control group (DR). In both groups, the hopeless tooth will be extracted atraumatically without raising a flap. The tooth is replaced by an immediately placed implant. The test implants will be restored with a provisional crown immediately, which will be replaced by a permanent crown at 4 ± 1 month (crown impression visit) after implant placement. The

control implants will be restored at 4 ± 1 month (crown impression visit) after the surgery.

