Subjects can be considered a screen fail at any study visit prior to the surgery and up until the time that the implant is placed and deemed stable. All screen failed subjects will be replaced.

Inclusion and exclusion criteria

Inclusion Criteria

• Male or female, aged ≥ 21• A minimum dentition of 20 permanent teeth (including natural rooted teeth or dental implants; pontic of a fixed bridge is not considered a tooth)• A maxillary premolar, canine, lateral incisor or central incisor with a hopeless prognosis• Presence of adjacent teeth and enough clearance for an implant crown• Presence of sufficient bone apical to the root apex of the hopeless tooth

Exclusion Criteria

Systemic criteria:

- Current heavy smokers (>10 cigarettes per day) or heavy smoker who quit less than 1 year ago
- Pregnant or plan to get pregnant or lactating mothers
- Current alcoholism or drug abuse
- Diseases of the immune system or any medical condition that may influence the outcome (uncontrolled diabetes ($\text{HbA1c} > 7$), neurologic or psychiatric disorders, systemic infections, ...)
- Radiation therapy in the head and neck area within 3 years
- Current use of oral bisphosphonates for >3 years
- History of IV bisphosphonates use
- Other medical conditions that may contradict an implant surgery

Intraoral criteria:

- Area of study is adjacent to an existing implant
- Acute infection at/or adjacent to the extraction site (e.g., sinus tract, swelling)
- Observable gingival changes due to use of medications known to affect the periodontal status (calcium antagonists, anticonvulsives, immunosuppressants, anti-inflammatory medications...)

- Untreated deep carious lesions or defective restorations that can potentially exacerbate during the course of the experiment
- Uncontrolled periodontal disease
- Poor oral hygiene (>20% FMPS)

CBCT criteria:

- More than 4mm of buccal plate dehiscence is present on the CBCT scans

Intraoperative criteria:

- More than 4 mm of buccal plate dehiscence is present once the tooth is extracted

The screening visit (V1)

All participants will receive an informed consent form that explains the aims, courses, and potential benefits/risks of this study. They will be given no limit of time to read through it. The research team members will answer any questions regarding this study. Any research related activity will not be initiated unless they sign the consent form.

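### Subjects are randomised before surgery while eligibility and replacement stay open until the implant is judged stable, and nothing in the plan keeps the arm from the surgical team

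*Combined protocol and SAP*

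**What the plan says.** Two places put assignment before surgery. The General Investigational Plan says "The subject will be randomly assigned before the surgery visit", and the Pre-implant placement visit (V3) section says "Eligible subjects will be randomly assigned to one of the two groups after V3".

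Eligibility closes later. Under III. Treatment, A. Patient selection, a subject can be a screen failure "up until the time that the implant is placed and deemed stable. All screen failed subjects will be replaced". The exclusion criteria include an intraoperative one, more than 4 mm of buccal plate dehiscence seen at extraction. The Schedule of Events marks an eligibility screen at V4 and lists inadequate bone there as a reason for withdrawal by the PI.

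The Implant and bone surgery (V4) section adds two removals. For plate loss: "Subjects who lose more than 4mm of buccal plate after extraction will be excluded from the study at this time". For the test arm only: "The test implant that does not achieve 30 N-cm will be treated as a control implant and excluded from the study". Management of adverse events gives a 10-20% rate of implants without primary stability and says those participants are withdrawn.

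Patient selection gives forty randomised, 20 per arm. No section describes allocation concealment, the arm to which a replacement goes, or an analysis set.

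**The concern.** Randomisation protects the comparison only if membership of the trial is settled before anyone who judges eligibility can know the arm. Here the last eligibility judgements follow assignment, and the plan does not keep the arm from those who make them. Plate loss has a numeric limit but needs judgement near it. Stability has no stated criterion that applies to both arms.

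The judgement on plate loss matters for the outcome. The Introduction links buccal plate thickness to soft-tissue stability, and buccal wall defects to advanced recession. Recession is part of the primary objective and the basis of the sample size. If borderline cases were handled differently by arm, the two groups could differ on a prognostic factor. Calling those subjects screen failures would take them out of the randomised denominator, so a reader of the results could not see it.

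This is separate from the 30 N-cm rule. That rule makes exclusion differ by arm outright, but plate loss and stability would still be judged after assignment if it were the same in both arms.

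**Working it through.** **Order of events, from the sections cited above**

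1. V2: CBCT; more than 4 mm of buccal dehiscence excludes.
2. After V3: assignment.
3. V4: extraction; plate judged against 4 mm; guided implant placement; stability assessed.
4. V4: the arms diverge, with a provisional crown (test) or a healing abutment (control).

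The eligibility checks in step 3 come after assignment but before the treatments differ. Assignment could therefore be revealed between steps 3 and 4 without changing the surgical sequence.

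**The plan's own sample size**

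Inputs (Sample Size section): difference 0.8 mm, SD 0.8 mm, 80% power, 5% alpha (two-sided assumed), 10% dropout.

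- Normal approximation: 2 × (1.960 + 0.842)² × (0.8/0.8)² = 15.7, so 16 per arm; 16/0.90 = 17.8, so 18 per arm, 36 in total.
- Noncentral t: 17 per arm; 17/0.90 = 18.9, so 19 per arm, 38 in total.

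The stated 40 is consistent with the t calculation. It allows for 10% dropout and for nothing else.

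**Randomised against treated**

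Let f be the proportion without primary stability, 10% to 20% (Management of adverse events). Assume that all of it arises at V4, applies equally to both arms, and is separate from dropout. This is an upper-end assumption for this source of loss.

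| | f = 10% | f = 20% |
|---|---|---|
| Randomised to give 40 treated, 40/(1 − f) | 44.4, so 45 | 50 |
| Treated if 40 randomised, no replacement, 40(1 − f) | 36 | 32 |
| After 10% dropout | 32.4 (16.2 per arm) | 28.8 (14.4 per arm) |
| Power by t | 78.7% | 73.4% |
| Chance of no failure in 40, (1 − f)^40 | 1.5% | 0.01% |

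For comparison, 18 per arm gives 83.0% power by t. Exclusions for plate loss or for the 30 N-cm rule would add to the losses; the documents give no rate for either.

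**Bias, as illustration only**

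Suppose that knowing the arm led to exclusion of 10% of one arm, and that their recession would have been 1 SD (0.8 mm) above the rest. That arm's mean would shift by 0.10 × 0.8 = 0.08 mm. Against the 0.8 mm target this is 10%. Against the standard error of the difference at 18 per arm, 0.8 × √(2/18) = 0.27 mm, it is about 0.3 standard errors. Neither the 10% nor the 1 SD comes from the documents.

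**The case against.** Several points on the other side have force.

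- **The number forty.** A reader might infer that forty randomised and forty treated cannot both be true. The documents do not support that. The counts agree if nobody fails at V4, and forty may be meant as the net target that replacement fills. What stands is that agreement is unlikely on the plan's own rate if failures fall at V4.
- **The 10-20% rate.** It appears under adverse events, after the post-operative visits, and mentions infection and removal in a separate surgery. The Schedule lists loose implants as a reason for withdrawal only from V5. The V4 section does foresee absent stability during surgery, so some of the rate belongs there, but the share is not given. Nor does that section say such subjects are replaced. The range of 45 to 50 is therefore not a forecast.
- **Bias.** A reader might infer that the comparison is biased. Exclusions on features judged before the arms diverge, if applied alike, do not bias it. Bias needs someone who knows the arm and acts on it. The documents are silent on the first and show nothing of the second.
- **Room for discretion.** The CBCT screen removes clear dehiscence before assignment, so the V4 check is a second look at a numeric limit. A reader might also infer that knowing the arm would alter implant position. Computerised guides made from the CBCT set that position in both arms, so the point is not relied on here.

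The order of events, the open window, the replacement rule and the absence of any concealment step remain.

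**Conclusion.** The concern holds in a limited form. The documents state that assignment precedes the last eligibility checks and that screen failures up to a stable implant are replaced. They describe nothing that hides the arm from those who make the checks. Selection with knowledge of the arm is therefore possible; whether it would occur, and how large any bias would be, cannot be derived from the plan.

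The stated number randomised is unlikely to equal the number treated. The figures of 45 to 50 randomised, or 36 to 32 treated, rest on the whole 10-20% falling at V4 and applying to both arms; the first pair also assumes replacement. The power calculation itself is not in error.

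Patient selection has V4 failures replaced, while the V4 and adverse-event sections have them excluded or withdrawn. These must be reconciled, because they decide who counts as randomised. The change should be made: the weakness is real and cheap to remove.

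**What to change.** Replace the V3 sentence, and the matching one in the General Investigational Plan, with: *Assignment is revealed during V4, by opening the next sealed, sequentially numbered envelope, only after the tooth is extracted, the buccal plate is assessed, the implant is placed and its stability is recorded. All intraoperative eligibility checks are applied alike to both arms before the envelope is opened.*

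Subjects who fail earlier are then true, unrandomised screen failures and can be replaced without touching the randomised comparison; forty randomised can mean exactly that.

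This alone is not enough. The test-only 30 N-cm exclusion would still operate after randomisation. It must be reconciled with the stability condition in Patient selection so that no eligibility exclusion follows assignment; the clinical threshold is for the investigators to decide. The terms replaced, excluded and withdrawn should be aligned at the same time.

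If the provisional crown or temporary denture has to be prepared ahead, keep assignment after V3, have the coordinator withhold it from the surgeon until stability is recorded, and report every randomised subject by arm. Subjects failing at V4 would then still be randomised, so the number randomised should allow for that loss.

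Cost: a protocol amendment and envelopes, with no added visits or patients. Provisional crown materials must be on hand for every subject, or the crown made within the 48 hours by which the Introduction defines immediate restoration. Temporary denture arrangements must not reveal the arm.
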